2.1 Lay Summary & Aims

Medicine has traditionally been learned through the face-to-face lecture, clinical experience on hospital wards, and student self-direction to additional resources such as textbooks and clinical guidelines. Recently educators have sought to improve student learning by providing adjuncts to these methods. The rapid development of computerized technology has seen the emergence of online educational packages in medical programs throughout the world.

‘PlayMed’ is a serious computer game that has been developed to teach paediatrics to medical students. It allows students to learn and apply clinical algorithms for managing patients in a safe, simulated environment. Preliminary data gained from a pilot study suggests that PlayMed improved students’ knowledge of asthma management. However, the efficacy of PlayMed as a learning tool has not been tested against alternative online educational tools, therefore we propose to conduct a randomized control trial of PlayMed using an online educational package as a control. Furthermore, we aim to assess the utility of PlayMed in different populations including nurses and doctors.

We have targeted two common and important paediatric clinical presentations (asthma and seizures) as the focus of our teaching and assessment in this study. It is likely that students will be exposed to both of these conditions during their clinical attachments; the acute management of both conditions is outlined in current NSW Health Paediatric Clinical Practice Guidelines (CPG); and both asthma and seizure disorders are listed in the Australian Curriculum Framework For Junior Doctors. The current UNSW Phase 3 Children’s Health course includes one lecture on each clinical problem.

Under the “G4MER” Program, we plan to perform a series of randomised control trials to see if PlayMed is an effective teaching adjunct to our standard course(s), and if this game is more effective than other online packages for medical students, doctors and nurses. We hypothesise that participants exposed to the game (in addition to standard teaching) will demonstrate superior knowledge and clinical skills compared to those exposed to the alternative online packages, and to those who only receive standard teaching. Additionally, we hypothesise that increased time spent playing the game will improve performance in knowledge-based and clinical assessments.

2.2 Background Literature Review

The efficacy of both online learning and simulation-based teaching have been well established in Medical Education.^{1,2} Online learning is most effective when students are required to interact either with the package or with each other, and feedback is provided.¹ Simulation is effective as it allows learners to engage in repetitive practice, in a safe environment, with a degree of clinical variation and a range of levels of difficulty. Timely feedback is also vital to effective learning.³

Computer-based simulation games can be defined as instruction delivered via personal computer that immerses trainees in a decision-making exercise in an artificial environment in order to learn the consequences of their decisions.⁴ Computer-based simulation games combine the most effective elements of both online learning and simulation - the online environment provides an easily accessible, interactive yet safe space for students; feedback is provided to the student, and clinical variation with a range of levels of difficulty can be provided.

Little empirical evidence on the effectiveness of educational video games on students' educational outcomes is available. A recent innovative study at UNSW by Dobrescu et al⁵ compared the effectiveness of teaching introductory economics via a video game or traditional textbook learning. This study suggested that there was no difference in exam performance for either modality; however, the video game was considerably more enjoyable as a learning tool. To our knowledge there are no educational role-playing games available on the market which targets the education of medical or nursing students. Currently online learning packages for paediatric clinical practice guidelines are available through HETI Online (<https://hetionline.cit.health.nsw.gov.au/>). At present these are not part of mandatory training.

The development of an online game is an expensive and resource intensive process but may well be an effective adjunct to current teaching programs. We wish to test this product to see if further investment is worthwhile.

3. Study Protocol

3.1 Research Design Outline

The “G4MER” Program aims to perform a series of randomised control trials on different groups at Sydney Children’s Hospital Randwick:

- (1) **Study 1A** (Formerly titled “Serious Games in Medical Education – a Randomised Control Trial”) involves Phase 3 medical students at UNSW having 8 weeks access to the game, an Online Package (OP) or NSW State Guidelines on Asthma and Seizure management (control). Students are then assessed using multiple choice questions (MCQ) and two observed structure clinical examination (OSCE) stations (detailed below).
- (2) **Study 1B** is also a randomised control trial similar in design to Study 1A, however it will involve doctors and nurses employed at Sydney Children’s Hospital. PlayMed will be compared against the HETI Learning Path Paediatric Clinical Practice Guidelines (Online Package for staff).
- (3) **Study 2A** is identical to Study 1A except participants will have 5 days access to their educational tool. Participants will then undergo the same assessment using multiple choice questions (MCQ) and two observed structure clinical examination (OSCE) stations.
- (4) **Study 2B** is identical to Study 1B except participants will have 5 days access to their educational tool. Participants will then undergo the same assessment using multiple choice questions (MCQ) and two observed structure clinical examination (OSCE) stations.

The proposed study designs are all investigator blinded randomised control trials. Participants may only be involved in Study 1 or Study 2, not both.

3.2 Participants

Studies 1A and 2A

Medical students in their second phase (years 3 or 4) and final phase (years five and six) of their medical degree (the BMed/MD program) at UNSW, currently completing their Children's Health course at Sydney Children's Hospital, will be eligible to participate in this study.

Studies 1B and 2B

Doctors and Nurses employed at Sydney Children's Hospital will be eligible to participate in this study.

Study investigators will not be eligible to participate.

Participants will require a personal computer and access to the internet to participate.

3.3 Recruitment

Studies 1A and 2A

All students enrolled in the UNSW Phase 3 Children's Health course will be informed of the study during their face-to-face orientation by the Course co-ordinators (the course co-ordinators are neither involved in the research nor in student assessment); a slide outlining

what will be said has been attached. Students will be told that a computer game, developed to teach medical students paediatrics, is being tested by randomised control trial, and that volunteer Children's Health students are invited to participate. Additionally, they will be informed that all participants will have the opportunity to go to the simulation laboratory and manage a sick child as a formative assessment with feedback provided.

Students will be informed at this time that their decision to participate, or not to participate, in the study, will not affect their relationship with the university or with the hospital in any way. Neither will the results of their study assessment contribute to their summative course assessment. Feedback with the answers to the MCQs will be available at completion of study, which should be before their end of 6th year summative assessment.

The participation information and consent sheet will be distributed which details including inclusion and exclusion criteria. Interested students will be invited to attend an information session scheduled in a break in their lecture timetable, this information session will allow study co-ordinators to answer questions from potential participants.

Studies 1B and 2B

All medical and nursing staff at Sydney Children's Hospital will be approached during Grand Rounds, lunchtime and evening teaching sessions, and via a concurrent staff email. Study advertisement posters will also be placed around the hospital. Recruitment will occur periodically throughout the calendar year (4 time points). Participants will be told that a computer game, developed to initially teach medical students paediatrics is being tested by randomised control trial, and that volunteer medical and nursing staff are also invited to participate. Given that the teaching tools are aimed at patient management, they are appropriate to administer to medical and nursing staff. Furthermore, the HETI Online Paediatric Clinical Practice Guidelines and NSW state guidelines are applicable to staff at

Sydney Children's Hospital. Additionally, they will be informed that all participants will have the opportunity to go to the simulation laboratory and manage a sick child as a formative assessment with feedback provided.

Participants will be informed at this time that their decision to participate, or not to participate, in the study, will not affect their relationship with the hospital in any way.

Feedback with the answers to the MCQs will be available at completion of study. Participants will be asked not to share the answers with other staff.

The participation information and consent sheet will be distributed which details including inclusion and exclusion criteria. Interested staff will be invited to attend an information session scheduled at Grand Rounds, this information session will allow study co-ordinators to answer questions from potential participants.

All participants will have to return a signed consent form to the student coordinators prior to random allocation to a study group.

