3.7 Sample Size

Study 1A

GLIMMPSE (<http://glimmpse.samplesizeshop.org/#/>) was utilised for sample size calculation with equal group sizes (i.e ratio of groups 1:1:1). In our initial pilot study, the mean quiz scores were 7.0 (SD 1.4) and 6.0 (SD 1.4) for the PlayMed and control cohorts (standard teaching only) respectively.⁶ If we assume that students in the OP cohort will achieve quiz scores of 50% the difference between PlayMed and controls (i.e. score of 6.5), then the following sample size is required:

- A total of 54 subjects (i.e. 18 in each group) to be able to reject the null hypothesis that the population means of the experimental and control groups are equal with probability (power) 0.8. The Type I error probability associated with this test of this null hypothesis is 0.05.
- Assuming a total drop-out rate of 20%, we will recruit 22 subjects for each group, i.e. 18 PlayMed, 18 OP and 18 controls.

Study 2A

Given we have no preliminary data for doctors and nurses, the same sample size estimate will be used for this study. We will recruit 22 subjects for each group, i.e. 22 PlayMed, 22 OP and 22 controls.

Studies 1B and 2B

The same sample size estimates will be utilised for these studies. For each study we will recruit 22 subjects for each group, i.e. 22 PlayMed, 22 OP and 22 controls.

4. Statistical Analysis Plan (SAP)

All Studies

Descriptive and inferential statistics will be used. Normally distributed data will be presented by mean and standard deviation (SD) and non-normally distributed data will be presented by median and interquartile range (IQR). Binary and categorical data will be presented using counts and percentages. R v3.4.4 will be used for all statistical analyses.

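### Studies 1B and 2B admit staff of any grade, but no visible text records grade and the unadjusted primary test uses neither grade nor the doctor/nurse stratum, so power is lost if grade predicts score

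*Combined protocol and SAP*

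**What the plan says.** **Who enters.** Section 3.2 states for Studies 1B and 2B that "Doctors and Nurses employed at Sydney Children's Hospital will be eligible to participate in this study". The only exclusion given there is "Study investigators will not be eligible to participate". Section 3.3 adds that "All medical and nursing staff at Sydney Children's Hospital will be approached during Grand Rounds, lunchtime and evening teaching sessions".

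**What the size rests on.** Section 2.1 describes PlayMed as a "serious computer game that has been developed to teach paediatrics to medical students". In the pilot cited in section 3.7, "the mean quiz scores were 7.0 (SD 1.4) and 6.0 (SD 1.4) for the PlayMed and control cohorts (standard teaching only) respectively". Section 3.7 then assumes that "students in the OP cohort will achieve quiz scores of 50% the difference between PlayMed and controls (i.e. score of 6.5"), and arrives at "A total of 54 subjects (i.e. 18 in each group) to be able to reject the null hypothesis" with 80% power. For 1B and 2B it says "The same sample size estimates will be utilised for these studies" and sets 22 per group. It also concedes that there are no preliminary data in doctors or nurses, although that sentence is printed under Study 2A, a student study.

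**What is measured and how it is compared.** Under section 3.6, staff sit a 15-point MCQ and a 50-point OSCE; students sit 10 and 30 points. Section 3.4 has one staff factor, job (doctor or nurse), and assigns it to Studies 2A and 2B. What it says is kept at allocation is an ID, the student or staff number and the group. Section 4.1 compares two arms at a time by a two-sample t-test or Mann-Whitney test, with no covariate or stratum term. Neither grade nor years of experience appears in sections 3.2 to 3.7 or 4.1 to 4.3, and no test is given before the intervention.

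**The concern.** A new graduate nurse and a consultant can enter the same study and sit the same tests. Grade is then a plausible predictor of both primary outcomes, and with no baseline score nothing else in the plan stands in for prior knowledge. The job stratum separates doctors from nurses, not junior from senior within either profession, and it is not carried into the analysis. In an unadjusted comparison, whatever variance grade explains stays in the error term.

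At stake is power in two small studies whose size was borrowed from a student calculation. A two-level factor known before randomisation could recover part of it.

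**Working it through.** **Inputs from the plan.** Difference 1.0 (PlayMed vs control), 0.5 (PlayMed vs online package), SD 1.4, alpha 0.05, 18 evaluable and 22 recruited per group (section 3.7). Two-sided testing is assumed, since sidedness is not stated. The planning scale is taken as 10 points, the length of the student MCQ. I use 18 per arm because that is what section 3.7 expects after drop-out; the group-mean imputation in section 4.3 adds rows but no information.

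**Input not in the plan.** The effect of grade on score. It is assumed over a range.

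**Step 1: the plan's own figure.** By the normal approximation, n per group = 2 × (1.96 + 0.842)² × 1.4² / 1.0² = 30.8, so 31; the t-test needs 32. The stated 18 does not reproduce. At 18 per arm, power is 55% for a difference of 1.0 and 18% for 0.5; at 22 it is 64% and 21%. That shortfall is a separate matter. Here it only sets the starting point of 55%.

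**Step 2: grade explains part of a total SD of 1.4.** If it explains a share R², the SD after adjustment is 1.4 × √(1 − R²). Power is for 18 per arm, ignoring the small loss of degrees of freedom.

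| R² | SD after adjustment | Power, difference 1.0 | Power, difference 0.5 |
|---|---|---|---|
| 0 (unadjusted) | 1.40 | 55% | 18% |
| 10% | 1.33 | 59% | 20% |
| 25% | 1.21 | 67% | 23% |
| 50% | 0.99 | 84% | 31% |

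**Step 3: grade adds to a within-grade SD of 1.4.** Take half junior and half senior, with a gap of D points. The variance between grades is D²/4 and the total SD is √(1.4² + D²/4).

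| D | Total SD | Unadjusted power, difference 1.0, 18 per arm | Adjusted |
|---|---|---|---|
| 1 | 1.49 | 50% | about 55% |
| 2 | 1.72 | 40% | about 55% |
| 3 | 2.05 | 30% | about 55% |

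**Step 4: is chance imbalance an extra harm?** With D = 2, the SD of the error from unequal grade mix between two arms is 1.0 × √(2/18) = 0.33. Ordinary sampling error is 1.4 × √(2/18) = 0.47. Together, √(0.33² + 0.47²) = 0.57. The t-test standard error on the total SD is 1.72 × √(2/18) = 0.57. They are the same variance, so step 3 already counts the imbalance.

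**Step 5: the staff scale.** If effect and SD both stretched in proportion to 15 points (1.5, 0.75 and 2.1), the standardised effects and the powers would not change. Nothing in the documents shows that they do, and no planning figure is given for the OSCE.

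**The case against.** The strongest reply is that the size of the problem is not in the documents. Neither D nor R² is given, a 50:50 split maximises the variance between grades, and at D = 1 or R² = 10% the change is only about 5 points of power. That stands: the figures illustrate a range and are not an estimate. Broad eligibility also fits the aim in section 2.1 of testing the game in doctors and nurses, and section 3.7 openly says that staff data are lacking. That stands too, so nothing here asks for narrower eligibility.

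A reader might infer four stronger things that the documents do not support.

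- *A chance excess of senior staff biases the result or rivals the planned effect.* Under randomisation the imbalance is part of the t-test standard error (step 4), so it brings neither bias nor type I error inflation. Whether it is large against 0.5 or 1.0 depends wholly on the assumed gap.
- *An imbalance could never be corrected.* Section 3.4 ties each ID to a staff number and section 5.2 keeps the linking key for seven years, so grade may be retrievable. A later adjustment would be post hoc, and so weaker than a pre-specified one.
- *Grade is certainly unrestricted and uncollected.* Section 3.3 refers to inclusion and exclusion criteria in an information sheet that is not available here. The claim covers only the visible text.
- *Senior staff will score near the ceiling.* No staff scores or test difficulty are given, and a grade term would not cure a ceiling anyway.

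**Conclusion.** The point holds as one of precision. Staff eligibility is open on grade, no visible text records grade, and section 4.1 ignores both grade and the job stratum. If grade predicts score, adjustment gains power for a difference of 1.0 at 18 per arm: from 55% to between 59% and 84% if grade explains 10% to 50% of a fixed total SD of 1.4, or from between 50% and 30% back to about 55% if a gap of 1 to 3 points adds to that SD. These ranges rest on assumed grade effects, two-sided tests and student figures on a 10-point scale. If grade does not predict score, almost nothing is gained and almost nothing is lost.

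Adjustment does not rescue PlayMed vs online package: even at R² = 50%, power for a difference of 0.5 is about 31%.

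One inconsistency needs settling whatever the grade effect. Section 3.4 gives the job stratum to 2A and 2B, but the staff studies are 1B and 2B. Read literally, 1B is unstratified and a student study carries a staff stratum.

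**What to change.** 1. **Sections 3.3 and 3.4:** record job, grade and years of paediatric experience on the enrolment form before randomisation. Fix a junior/senior cut-point in advance within each profession, so that it is not chosen after scores are seen.
2. **Section 4.1, Studies 1B and 2B:** make the primary comparison of MCQ and OSCE a linear model with arm, job (the randomisation stratum) and junior/senior grade, on the staff scales of 15 and 50 points. The present unadjusted tests can stay as sensitivity analyses.
3. **Section 3.4:** reconcile the studies named for the job stratum with the staff studies, 1B and 2B.
4. **Section 3.7:** state that 22 per group in 1B and 2B is carried over from the student calculation on a 10-point test and has no staff-specific power.

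The cost is a short enrolment-form entry, a few sentences of text and two degrees of freedom per model (for a pairwise comparison at 18 per arm, 36 − 2 = 34 becomes 36 − 4 = 32). Eligibility and recruitment do not change. Grade is best captured before allocation, so this should be settled before staff are randomised.

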3.4 Randomisation

Students and Staff who consent to participate will be randomly allocated (within their study) to one of three groups (at a ratio of 1:1:1): the game, the OP, and no intervention (ie standard teaching only with NSW State Guidelines on Asthma and Seizure management provided).

Computer randomisation (<https://www.sealedenvelope.com>) and concealed envelopes will be used. We will use a separate unique block randomisation for each study (1A, 1B, 2A and 2B) with block sizes of 3, 6 and 9. A strata for job (Doctor / Nurse) will be incorporated for staff

in studies 2A and 2B. Participants will be allocated a unique identification number, and this will be recorded against their student or staff number and group allocation in an electronic database. This will be done by the student co-ordinators at the School of Women's and Children's Health to ensure the investigators remain blinded.

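### Section 3.4 assigns the doctor/nurse stratum to student Study 2A and omits staff Study 1B, and the primary tests in both staff studies ignore job

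*Combined protocol and SAP*

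**What the plan says.** Section 3.4 (Randomisation) gives each study its own block list and then adds: "A strata for job (Doctor / Nurse) will be incorporated for staff". The sentence continues "in studies 2A and 2B. Participants will be allocated a unique identification number". Study 1B is not named.

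Section 3.1 says that Study 2A "is identical to Study 1A except participants will have 5 days access to their educational tool", and Study 1A enrols medical students. Of Study 1B it says "it will involve doctors and nurses employed at Sydney Children’s Hospital". Section 3.2, under the heading for 1B and 2B, states "Doctors and Nurses employed at Sydney Children's Hospital will be eligible to participate in this study".

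Section 3.7 contains a similar mix-up. Under Study 2A it reads "Given we have no preliminary data for doctors and nurses, the same sample size estimate will be used for this study".

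Section 4.1 applies to all studies. It compares PlayMed with the online package and with the control guidelines, on MCQ and OSCE scores, by an unpaired t-test or a Mann-Whitney test. No job term, stratified test or job subgroup appears anywhere in section 4. On the unique ID, section 3.4 says "this will be recorded against their student or staff number and group allocation in an electronic database"; job is not mentioned there.

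**The concern.** There are two separate problems.

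The first is a contradiction about the design. The stratum is placed in a study with no doctors or nurses, and a study that enrols both is left out. This sentence is the only specification of stratification, so a reader cannot tell how the 1B list was built.

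The second remains even if the label is only a slip. The planners thought job important enough to stratify on, yet the primary tests take no account of it. If doctors and nurses score differently, that difference stays in the error term of two small trials. In a stratified trial the unadjusted standard error is then too large, so the test is conservative and loses power. In an unstratified trial the test has the right size but the estimate is less precise.

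**Working it through.** **1. The text, side by side**

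| Study | Population (3.1, 3.2) | Job stratum (3.4) | Job in primary test (4.1) |
|---|---|---|---|
| 1A | students | no | not applicable |
| 2A | students | **named** | not applicable |
| 1B | doctors and nurses | **not named** | no |
| 2B | doctors and nurses | named | no |

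**2. Inputs**

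- From section 3.7: means 7.0 and 6.0, SD 1.4, so the effect is 1/1.4 = 0.714 SD; 22 per group recruited; 20% dropout.
- Assumed, because the documents give neither: half doctors and half nurses; doctor-nurse gap g of 0, 0.5, 1 or 1.5 within-job SDs. The effect is borrowed from the student pilot and first read as within-job SDs.
- Figures are for PlayMed against control, two-sided 5%.

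**3. The plan's own figure**

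The 18 per group for 80% power is not reproduced. The normal formula gives 2 × (1.96 + 0.842)² × 1.4² / 1² = 30.8, so 31 per group; the t-test needs 32. Power is 0.55 at 18 and 0.64 at 22. That is a separate matter, but it makes 0.64 the baseline here.

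**4. Complete data, 22 per arm**

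*Stratified (11 doctors and 11 nurses per arm).* The true SE is √(2/22) = 0.302. The unadjusted variance estimate also contains 22 × (g/2)² / 21 = 0.262g². The SE is therefore too large by √(1 + 0.262g²) = 1.00, 1.03, 1.12, 1.26.

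*Unstratified.* The true SD of the difference is √((2/22)(1 + g²/4)) = 0.302, 0.311, 0.337, 0.377, and the t-test estimates it correctly. With job in the model it is about 0.305 at every gap.

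Simulation (60,000 runs per cell) agrees with both formulas and gives:

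| Gap (SD) | 0 | 0.5 | 1 | 1.5 |
|---|---|---|---|---|
| Stratified, unadjusted: type I error | 5.1% | 4.3% | 2.8% | 1.4% |
| Stratified, unadjusted: power | 0.64 | 0.62 | 0.54 | 0.44 |
| Stratified, job in model: power | 0.64 | 0.64 | 0.64 | 0.64 |
| Unstratified, unadjusted: power | 0.64 | 0.61 | 0.54 | 0.45 |
| Unstratified, job in model: power | 0.63 | 0.63 | 0.63 | 0.63 |

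Type I error is 4.9-5.1% for the unadjusted test in the unstratified design, and 4.9-5.2% with job in the model in the stratified design. A separate simulation using the planned blocks of 3, 6 and 9 gave the same pattern.

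**5. Planned dropout and section 4.3**

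20% of 22 is 4.4, so take 4 missing per arm and 18 observed, missing completely at random. Filling in the group mean gives a nominal SE of √((2/22)(34/42)) = 0.271 against a true √(2/18) = 0.333, a ratio of 0.81.

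| Gap (SD) | 0 | 0.5 | 1 | 1.5 |
|---|---|---|---|---|
| Stratified, imputed, unadjusted: type I error | 10.9% | 9.9% | 8.0% | 5.7% |
| Stratified, observed only, unadjusted: power | 0.55 | 0.53 | 0.46 | 0.36 |
| Unstratified, observed only, unadjusted: power | 0.55 | 0.52 | 0.46 | 0.38 |

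Unstratified and imputed, the unadjusted type I error is about 11%. With job added to imputed scores it is 10.7-10.9% in both designs. With job added and observed scores only, it is 4.9-5.1%, and power is 0.54-0.55 stratified and 0.53-0.54 unstratified.

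**6. The other reading of the SD**

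If 1.4 is the total staff SD, the unadjusted stratified test has power 0.64, 0.64, 0.65, 0.66 across the four gaps. With job in the model (noncentral t, 41 df) power is 0.64, 0.66, 0.73, 0.82.

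**7. Chance imbalance in an unstratified 1B**

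PlayMed and control differ by 4 or more doctors in 29% of randomisations with 33 doctors of 66, and in 22% with 16 of 66. A difference of 4 moves the contrast by 4/22 = 0.18 of the job gap.

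**The case against.** The strongest case is that this is a typing slip plus an optional efficiency gain. The sentence itself says the stratum is for staff, so a reader can guess that 1B and 2B were meant. Ignoring job causes no bias and no excess false positives. The larger losses need a gap of 1 SD or more, which the documents do not support; at 0.5 SD the loss is about 2 points of power. The effect and SD come from a student quiz, while staff sit a 15-point MCQ and an OSCE marked out of 50. All of this stands, and it limits the severity.

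Four narrower points also stand:

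- On the total-SD reading, power does not fall below the baseline as the gap grows. The loss is a gain forgone: 0.65 against 0.73 at a gap of 1, and 0.66 against 0.82 at 1.5. The adjusted test is still better.
- Chance imbalance in 1B is the source of its lower precision, not a second harm.
- Job must be known wherever the list is stratified, and the staff number may allow it to be looked up. Recording it explicitly is a safeguard.
- Adding job under the current 4.3 makes 2B worse: at a gap of 1, type I error goes from 8.0% to about 11%. The change works only together with a change to the imputation.

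None of this removes the contradiction in 3.4 or justifies leaving a stratification factor out of the analysis.

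**Conclusion.** The concern holds. As written, the stratum is assigned to a student study and Study 1B is not stratified by job; a slip for 1B and 2B is the likely explanation. In both staff studies the primary tests ignore job.

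The consequence is lost precision. On the within-job SD reading, with an even job mix and complete data at 22 per arm, the power lost in 2B is about 2, 10 and 20 points at gaps of 0.5, 1 and 1.5 SD (from 0.64 to 0.62, 0.54 and 0.44). In an unstratified 1B it is about 2, 9 and 18 points (from 0.63 to 0.61, 0.54 and 0.45). At zero gap there is no loss. The size therefore rests on a doctor-nurse gap and job mix that the documents do not give. The contradiction in 3.4 does not depend on any of these assumptions. The change should be made, but the staff trials are not invalid without it.

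**What to change.** 1. **Section 3.4, labels.** Name Studies 1B and 2B as the studies stratified by job. If the 1B list was generated without job strata, state instead that only 2B is stratified. Correct the reference to doctors and nurses under Study 2A in 3.7 at the same time.
2. **Section 3.4, data.** State that job (doctor or nurse) is recorded at enrolment for every participant in 1B and 2B.
3. **Section 4.1, Studies 1B and 2B.** Make each primary comparison the arm difference from a linear model of score on arm and job, with its 95% CI. On the rank route, use the van Elteren test stratified by job (not simulated here). State how Cohen's d is calculated once job is in the model.
4. **Section 4.3, Studies 1B and 2B.** Fit this model to observed scores, or use multiple imputation with arm and job in the imputation model. Do not apply it to group-mean-imputed scores.

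The cost is wording, one recorded variable, one degree of freedom and a different missing-data method. If there is no job gap, adjustment costs about 1 point of power in an unstratified 1B (0.637 against 0.628) and none in 2B.
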